The concept of the glycemic index has been expanded over the years, giving rise to mathematical products such as the glycemic load (GL), which is defined as the quantity and quality of carbohydrates consumed and estimates the total glycemic effect of the diet, for its obtaining it is necessary to multiply the amount of CHO contained in the food ingested by the GI value ($GL = GI \times \text{available carbohydrates}$).

The increase to the glycemic load is associated with an unfavorable physiological response, mainly for people living with diabetes, since blood glucose and insulin values rise sharply. Foods with $GL \leq 10$ are considered low GL and foods with $GL \geq 20$ are considered high GL.

OBJECTIVES

General objective

To evaluate the *in vivo* bioavailability of bioactive compounds from a *H. sabdariffa* beverage and their immunomodulatory potential against moderate inflammation caused by SARS-CoV2 as well as enzymatic inhibition of α -amylase and α -glucosidase enzymes *in vitro*.

Specific objectives

1. To perform HPLC-DAD-MS characterization of a *Hibiscus sabdariffa* hibiscus-based beverage.
2. To perform an acute single-blind clinical trial, administering a hibiscus drink to normal-weight adults.
3. To evaluate the bioavailability of organic acids and phenolic compounds in urine and plasma samples present in the *H. sabdariffa* beverage.
4. To evaluate the immunomodulatory potential of the metabolites identified as bioavailable in plasma samples.
5. To evaluate the enzymatic inhibition of α -amylase and α -glucosidase exerted by the digested, placebo and treatment beverages.
6. To evaluate the *in vivo* GR and IR of the placebo beverage and treatment beverage.

. GENERAL METHODOLOGY

First Stage

Obtaining hibiscus-based beverage and placebo.

The hibiscus-based beverages (H.sabdariffa) and placebo were obtained from the reformulated company NUTRIYÉ SAPI de CV, located in the city of Guadalajara, Jalisco, Mexico.

Participants.

Twelve normo-weight volunteer participants without any medical condition were included. The invitation to participate was made through ITESO's communications office, as well as through announcements in social networks. They were selected according to the following criteria:

Within the inclusion criteria to be considered are those mentioned in Table 4.2.

Table 4.2. Non-inclusion and inclusion criteria for volunteer selection.

Inclusion criteria		Non-inclusion criteria	

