Normolipidemia	Total cholesterol (plasma) < 200 mg/L-1	Hypertension	Hyperthyroidism
	Triglycerides < 150 mg/L-1	Diabetes	In diet
	Fasting glucose (plasma) < 100 mg/L-1	Smokers	Pregnant or lactating women
Normoglycemia	18.5 – 24.9	Cardiovascular disease	In medical treatment / supplements
BMI [kg/m2]	18 – 40	Secondary	Hepatic insufficiency

Abdominal circumference [cm].	Men < 90 Women < 80	hyperlipidemia Renal insufficiency	Infection / inflammatory disease (6 weeks prior to study)
Fat percentage [%] [cm]	Men < 19 Women < 33		
Systolic pressure [mmHg].	< 140		
Diastolic pressure [mmHg].	< 90		
Alcohol	Last consumption one week and a half		

The study adhered to the ethical principles for research on human subjects of the Declaration of Helsinki and was submitted to the ITESO Research Ethics Committee.

Acute Trial Clinical Intervention

An acute single-blind trial was conducted. Participants consumed a hibiscus-based drink (*H. sabdariffa*), or a 60ml placebo drink, and then received a Western-type diet characterized by excessive consumption of red meat, simple carbohydrates, ultra-processed products, colorants, saturated fats, refined sugars and very little intake of fiber and vitamins. After a washout period of more than 6 days, the participants underwent a second intervention with a different product from the first one (beverage to be evaluated or placebo, as appropriate), and the samples were repeated according to the following scheme

The protocol was previously explained to the volunteers and all those who give their written informed consent will be candidates to participate (Annex 1). On the day of the intervention, participants will arrive at 7 a.m., Mexico Central Time, with an overnight fast of 10-12h. They were requested a rest period of 30 min prior to blood pressure taking at the time of admission, in addition to the fact that they had to be seated, upright and with their feet on the floor during the process; the measurement was performed using a manometer on the left arm, elevated at the level of the heart (Gómez-León Mandujano et al., 2016).

Two types of sampling were performed:

(a) Urine.

For determination of phenolic compounds and organic acids in urine samples, a basal sample (T=0) was taken in a collection bottle. Once the hibiscus-based drink or placebo was ingested, samples were collected at the following times: 3h, 6h, 12h and 24h.

b) Blood

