For the studies of inflammation levels (IL-6 and TNF- α), and for the bioavailability of phenolic compounds and organic acids, blood samples were taken with the help of collecting tubes by venous puncture. Eight samples were taken, the first on arrival of the patients at basal time (T=B), then at 30 min (T=2), 1h (T=3), 1:30h (T=4), 2h (T=5), 3h (T=6), 4h (T=7) and 6h (T=8) after having ingested the hibiscus-based drink or the placebo.

In both interventions, patients received a Western diet (breakfast and lunch) characterized by excessive consumption of red meat, simple carbohydrates, ultra-processed products, dyes, saturated fats, refined sugars and very little intake of fiber and vitamins, adjusted to their physical characteristics, and supervised by a team of specialist nutritionists. The participants remained at the trial site without any type of physical exercise during the course of the study and in a relaxed environment with selected recreational activities; they also had a water fountain within their reach from which they could drink indefinitely and a team of medical services that was located at the trial site until its completion.

Sample handling.

For biochemical tests, plasma samples were separated by centrifugation at 3000 rpm for 10 minutes at 4 °C and divided into aliquots and stored at -20 °C until further analysis. On the other hand, urine samples were divided into aliquots and frozen at -20 °C until further analysis.

Extraction of phenolic metabolites and organic acids from biological samples.

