The inhibition of α -glucosidase of the beverages will be evaluated using the products of the different phases of the in vitro digestion and will follow the methodology described in the specifications of the α -glucosidase kit (Sigma-Aldrich #MAK123) where first 220 μ L of deionized water will be placed in a well of a reading plate and in another well 20 μ L of deionized water will be placed and 200 μ L of calibrator will be added to one of them. From the samples previously prepared in 50 mM phosphate buffer (pH 7.0) 20 μ L will be taken and placed in separate wells and 200 μ L of master solution will be transferred to each of them, the solution will be previously prepared with 200 μ L of p-nitrophenyl- α -D-glucopyranoside (NPG) buffer and 8 μ L of NPG substrate, then incubated at 37° C and absorbance will be measured at 405 nm using Synergy HT microplate reader

(Biotek Instruments, Inc., USA), the initial measurement (T-initial) will be read and after 20 minutes the final absorbance (T-final) will be taken.

The enzyme activity will be expressed in units per liter (unt/L) and calculated with the equation (Eq 6.2) where one enzyme unit is the amount of α -glucosidase that catalyzes the hydrolysis of 1 mM p -nitrophenyl- α -D-glucopyranoside per minute at pH 7.0.

$$\text{unt/L} = \frac{(\text{Abs final} - \text{Abs inicial})}{\text{Abs del calibrador} - \text{Abs del agua}} \times 250 \text{ unt/L} \quad \text{Ec 4.2}$$

Where:

Abs of the calibrator is the value for the calibrator at 20 minutes, Abs of the water represents the value of the water at 20 minutes and unt are units.

Evaluation of glycemic response.

To obtain the biological sample, a lancet will be used to puncture the thumb of the volunteer's finger and the sample will be collected on highly sensitive test strips for capillary glucose measurement of the OneTouch Ultra® System.

The portable system used for pre- and postprandial glucose measurement allows the monitoring of capillary glycemic response under experimental conditions for healthy subjects. With the use of this equipment, measurements will be obtained from t_0 (preprandial), and at 15, 30, 45, 60, 90 and 120 min (postprandial). The results will be expressed in mg/dL.

Insulin analysis.

Participants will be required to hold a hand warmer ($\sim 40^\circ\text{C}$) for 5 min before each capillary blood sampling, to stimulate peripheral blood flow.

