Blood samples (approx. 250 μL , 4-5 drops) will be drawn through finger pricks (OneTouch Ultra® lancets). Measurements over time will be similar to the glycemic response assessment technique. Samples will be placed in BD Microtainer SST tubes and kept at room temperature for 30 min. Samples will then be centrifuged

(5000 rpm, 25°C) for 10 min to obtain serum and kept in a freezer at -20 degrees Celsius until further analysis (Hossain et al., 2021).

Serum insulin concentrations will be analyzed using a two-site solid-phase enzyme immunoassay kit (Human Insulin ELISA Kit, Millipore, EZHI-14K), where the direct sandwich technique is used with two antibody solutions targeting insulin epitopes (Figure 6. 2) in such a way that the plate will be coated with a monoclonal antibody (capture) and then the sample will be added, so that the analyte of interest (insulin) will bind with the capture antibody and subsequently a horseradish peroxidase-labeled detection secondary antibody will be added, this antibody will bind to the antigens that will be in turn bound to the capture antibody, consequently will be added the substrate 3,3',5,5'- tetramethylbenzidine in buffer (TMB), forming a bluish coloration dependent on the insulin concentration, the reaction will be terminated by the addition of stop solution (HCl) obtaining as colored product (yellow) after acidification, which is quantifiable at 450 nm in a microplate reader (BioTek®, Synergy HT, Winooski, Vermont, USA). The results will be expressed in $\mu\text{U/L}$.

Statistical Analysis.

Statistical analysis: first stage

The normality of the data distribution will be evaluated by means of the Shapiro-Wilk test; if so, a Student's t-test will be used, or, on the contrary, a nonparametric Mann-Whitney test will be used to evaluate the statistical differences between the variables. The level of statistical significance will be a value of ($p < 0.05$). Statistical analysis will be performed with the STATISTICA program, version 10 (Statsoft.1984-2011 Inc., Tulsa, OK, USA).

Statistical analysis: second stage

Each sample will be considered as an experimental unit. Statistical analysis will be performed with the STATISTICA program, version 10 (Statsoft. 1984-2011 Inc., Tulsa, OK, USA). Differences in the response variables in the samples will be evaluated through a repeated-means ANOVA analysis. The level of statistical significance will be a value of ($p < 0.05$).

Calculation of the area under the curve.

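### First-stage comparisons: replace the normality gate between Student's t and Mann-Whitney with one pre-stated within-person analysis on a fixed scale

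*Combined protocol and SAP*

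**What the plan says.** *Statistical analysis: first stage* (Combined protocol and SAP) states "The normality of the data distribution will be evaluated by means of the Shapiro-Wilk test", and then "if so, a Student's t-test will be used, or, on the contrary, a nonparametric Mann-Whitney test will be used". The threshold for the comparison is p < 0.05.

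That section does not give:
- the level of the normality test;
- what it is applied to (values by drink, within-person differences, an AUC, or each time);
- whether the t-test is paired;
- any transformation, or a primary variable or time.

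The design is paired. Under *Participants*: "Twelve normo-weight volunteer participants without any medical condition were included". Under *Acute Trial Clinical Intervention*, after a washout, "the participants underwent a second intervention with a different product from the first one". Blood for IL-6, TNF-α, phenolic compounds and organic acids is drawn at baseline and at seven later times in each period.

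*Statistical analysis: second stage* uses a repeated-measures ANOVA with no normality gate. The plan does not list which outcomes belong to which stage.

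**The concern.** With 12 values per drink, a normality test often misses skew and sometimes flags normal data. Letting it pick the test means the data decide whether a result is about means or ranks. If the rule is run time by time, one marker could be compared by means at 1 h and by ranks at 2 h, and the estimates along the curve would not be comparable.

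The two branches matter as much as the gate. Mann-Whitney is a two-sample test, and so is Student's t unless it is declared paired. In a crossover the contrast is the within-person difference, so a two-sample test leaves between-person variation in the error term. Neither branch considers a log scale, although concentrations are often multiplicative. At stake is whether 12 people can show an effect on the first-stage markers.

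**Working it through.** **Inputs from the documents.** n = 12, each person on both drinks; 8 plasma samples per period (7 times for glucose); significance level 0.05. The documents give no power, effect size, SD or correlation, so there is no figure of the plan's own to reproduce.

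**Assumptions.** Two-sided 0.05; Shapiro-Wilk at 0.05 on each drink's values; Student's t unpaired; lognormal data unless stated. Period effects are not simulated.

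**1. Does the method change along a curve?** For truly normal data with independent times, the chance that at least one time is sent to Mann-Whitney is 1 − 0.95^(2 × times):
- 8 times: 1 − 0.95^16 = 0.56
- 7 times: 1 − 0.95^14 = 0.51

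Simulation with correlated times and periods gives 51–53% and 49–51%. For lognormal data and 8 times, the method is mixed in 70–76% of trials (CV 20%), 83–88% (CV 30%), 95–99% (CV 50%), 85–92% (CV 80%) and 56–62% (CV 120%). One lognormal sample of 12 is rejected in about 13–15% of cases at CV 30%, 28% at CV 50% and 49–51% at CV 80%. If the test were instead run once per time on the differences, the figure for normal data would be 1 − 0.95^8 = 0.34.

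**2. Type I error.** For the plan as written: 5.2–5.6% at between-period correlation 0, 1.0–1.2% at 0.5, and 0–0.1% at 0.8. It is not inflated; with positive correlation it is conservative.

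**3. Where does the power go?** The effect is set at 0.8886 SD of the log differences, so the paired log t-test has noncentrality 0.8886 × √12 = 3.08 and 80.0% power. Results at CV 50%, 4,000 runs:

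| Rule | corr. 0 | corr. 0.5 | corr. 0.8 |
|---|---|---|---|
| Plan as written (gate, two-sample tests) | 82.4% | 55.2% | 14.7% |
| Unpaired log t, no gate | 84.4% | 56.2% | 13.0% |
| Gate on differences, paired tests, raw scale | 76.2% | 75.2% | 74.3% |
| Paired log t, no gate | 80.5% | 80.2% | 79.9% |

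Rows 1 and 2 show the effect of gate plus scale with pairing ignored. Over CV 20–120% the difference is −4.3 to +2.0 points. Comparing rows 1 and 3 at correlation 0.5 and 0.8 shows the cost of ignoring pairing. Rows 3 and 4 show what remains once tests are paired; over all CVs that loss is:
- 0–1 point at CV 20%
- 2–3 at CV 30%
- 4–6 at CV 50%
- 7–11 at CV 80%
- 8–13 at CV 120%

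**4. Two strongly skewed examples.**

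A: between/within log-SD 0.7/0.35, ratio 1.4. Correlation 0.49/0.6125 = 0.80. SD of log differences 0.35 × √2 = 0.495. Standardised effect ln 1.4/0.495 = 0.336/0.495 = 0.68.

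B: 1.0/0.4, ratio 1.5. Correlation 1/1.16 = 0.86. SD 0.566. Standardised effect 0.405/0.566 = 0.72.

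Power, 3,000 runs:

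| Rule | A | B |
|---|---|---|
| Plan as written | 6.5% | 2.3% |
| Gate, paired tests | 46.0% | 48.1% |
| Signed-rank always, no gate | 45.7% | 48.3% |
| Paired log t | 56.7% (noncentral t: 57.4%) | 61.7% (noncentral t: 61.9%) |

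Repeat simulations put the last row at up to 58% for A and 63% for B. Removing the gate while staying with raw-scale differences changes almost nothing. The remaining 11 to 14 points come from the scale.

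**5. If the data are not skewed.** With additive normal data (assumed mean 1.2, between/within SD 0.30/0.25 and 0.35/0.30), the gated paired rule gave 49.6% and 55.3%, against 44.6% and 48.7% for the paired log test.

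**The case against.** The strongest reply is that the text supports less than a reader might infer from it. Several such readings fail or need a condition:

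- *The test is run separately for every variable and time, on raw values.* The plan says neither. The figures in step 1 are conditional on that use. What stands is that the unit is left open until the data are seen.
- *The gate inflates false positives.* It does not (step 2).
- *The gate causes the power loss.* It does not. Always using signed-rank gives the same power as the gated paired rule. The losses come from ignoring pairing and, second, from the raw scale.
- *The rule governs every curve in the study.* It covers the first stage only. Glucose and insulin may fall under the second-stage ANOVA.
- *The documents show that a log scale is needed.* They give no variance or distribution for any marker. The gain is 0–3 points at CV 20–30%, and it reverses for additive normal data.

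It is also fair to say that naming a within-person analysis repairs most of the damage by itself. That is correct, and it is why the fix starts there. The t-test might be intended as paired; if so, the loss falls mainly on outcomes sent to Mann-Whitney, whose two-sample form is not in doubt.

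**Conclusion.** The point holds in a limited form. The first-stage rule lets a normality test on about 12 values per drink choose the comparison, with its unit unstated. If applied to both drinks at each time, a mixed method along one curve is about as likely as not for normal data, and more likely than not for the lognormal settings tried. The gate does not threaten type I error and costs little power.

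The material loss is from two-sample tests in a crossover: 80% falls to about 55% at correlation 0.5 and about 15% at 0.8. In the skewed example A, power is about 6% instead of 57–58%. With paired tests in place, the raw scale costs a further 0–14 points if the data are lognormal, and nothing if they are additive and normal. All power figures rest on assumed CVs, correlations and distributions, and the plan-as-written figures also assume an unpaired t-test. This is a low-priority improvement to the SAP, and the pairing is its most important part.

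**What to change.** For first-stage outcomes:

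1. Delete the Shapiro-Wilk gate and the choice it controls.
2. Pre-state one within-person analysis: a paired comparison, or a mixed model with treatment, period and sequence.
3. Fix the scale in advance. Use logs for cytokine and metabolite concentrations and total AUCs, reported as hibiscus/placebo ratios with 95% confidence intervals.
4. Keep the paired signed-rank test as a sensitivity analysis, and as the main analysis for compounds mostly undetected on placebo.
5. Do not log incremental AUCs by default. *Calculation of the area under the curve* discards area below the fasting level, so zero is possible. Leave these untransformed or state a rule for zeros.
6. List which outcomes belong to the first stage.

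The cost is SAP wording only; no visits, samples or participants change. The downside is that results read as ratios, and undetected or zero values need a rule written down before the data are seen.

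### The first-stage analysis names an independent-samples test (Mann-Whitney), and a t-test not stated to be paired, for a crossover in which the same 12 people take both drinks

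*Combined protocol and SAP*

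**What the plan says.** The Participants section reports "Twelve normo-weight volunteer participants without any medical condition were included". Under Acute Trial Clinical Intervention each volunteer takes one drink and then: "After a washout period of more than 6 days", "the participants underwent a second intervention with a different product from the first one". Sampling is repeated in the second period, so each hibiscus value has a placebo value from the same person at the same time point.

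Statistical analysis: first stage begins with a Shapiro-Wilk test on the distribution of the data. If normality holds, "if so, a Student's t-test will be used", with no mention of pairing. Otherwise "a nonparametric Mann-Whitney test will be used to evaluate the statistical differences between the variables". The significance level is 0.05, and sidedness is not given.

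Statistical analysis: second stage states "Each sample will be considered as an experimental unit" and "Differences in the response variables in the samples will be evaluated through a repeated-means ANOVA analysis".

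Neither section says which endpoints belong to which stage. In the methodology, the only stage heading is First Stage, and the crossover is described beneath it.

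**The concern.** Mann-Whitney compares two independent groups and makes no use of the link between a person's two results. The t-test admits two readings:

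- **Unpaired.** Both branches ignore the design.
- **Paired.** The plan drops the pairing whenever Shapiro-Wilk rejects, so the outcome of a normality test decides whether the crossover structure is used.

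On either reading, Shapiro-Wilk is aimed at the wrong quantity. A paired analysis needs the within-person differences to be roughly normal, not the raw values.

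Removing between-person variation is the main statistical gain of a crossover. With 12 participants and no sample-size justification, losing that gain could turn a real effect on metabolites, IL-6, TNF-alpha, glucose or insulin into a null result that cannot be interpreted.

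The second-stage ANOVA could keep the within-person structure. Calling each sample the experimental unit leaves it unclear whether participant is the subject factor.

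**Working it through.** **Inputs from the documents.** n = 12 (Participants); both drinks taken by each person (Acute Trial Clinical Intervention); alpha 0.05 (Statistical analysis: first stage). There is no stated power, effect size, SD or correlation, so no planned figure exists to reproduce.

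**Assumptions.** Two-sided test; equal SD under both drinks; within-person correlation rho varied, because the documents do not give it.

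**Why the unpaired test is miscalibrated.** The true standard error of the mean difference is SD × √(2(1−rho)/12). The unpaired test uses about SD × √(2/12), so its statistic is too small by a factor of about √(1−rho): 0.71 at rho 0.5 and 0.55 at rho 0.7. In return it has 22 rather than 11 degrees of freedom, so its critical value is 2.074 rather than 2.201. The two effects roughly balance when √(1−rho) = 2.074/2.201 = 0.942, that is rho ≈ 0.11. Above that, pairing wins.

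**Effect held at a fixed paired power.** The noncentral t gives 80% paired power at n = 12 for an effect of 0.889 SD of the differences. The figures are from simulation. Mann-Whitney power depends only on ranks, so it is the same for normal data and for lognormal data with the effect set on the log scale.

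| rho | Unpaired t: type I error | Unpaired t: power | Mann-Whitney: power |
|---|---|---|---|
| 0 | 5.0% | 84% | 80% |
| 0.1 | 4.1% | 81% | 77% |
| 0.2 | 3.1% | 77% | 73% |
| 0.3 | 2.2% | 72% | 68% |
| 0.5 | 0.9% | 57% | 52% |
| 0.7 | 0.2% | 30% | 27% |
| 0.8 | 0.04% | 13% | 13% |

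Across all rows the paired t-test keeps 80% power and about 5% type I error. The signed-rank test keeps 76% power and 4.1–4.4% type I error. On raw lognormal differences its power is 71% falling to 68%. Mann-Whitney type I error is about 2% at rho 0.3, 0.9% at 0.5 and 0.2% at 0.7.

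**Effect held at a fixed raw size, 0.8 SD of a single measurement (power).**

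| rho | Unpaired t | Mann-Whitney | Paired t | Signed-rank |
|---|---|---|---|---|
| 0 | 46% | 42% | 43% | 39% |
| 0.3 | 45% | 41% | 57% | 52% |
| 0.5 | 46% | 41% | 71% | 67% |
| 0.7 | 45% | 41% | 90% | 87% |
| 0.8 | 46% | 42% | 98% | 97% |

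**Sign of the correlation.** At rho −0.3 the unpaired tests are anti-conservative: type I error is 8.2% for t and 7.4% for Mann-Whitney. The paired t-test stays at 5.1%.

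**The case against.** **The crossover outcomes may belong to the second stage.** They are time courses: eight blood draws, five urine samples, and seven glucose and insulin times. A repeated-measures ANOVA suits them, and the t-test or Mann-Whitney rule might cover only beverage or in vitro comparisons, where pairing by person does not arise. This stands as uncertainty, because the plan assigns no endpoints. Against it, the crossover sits under the First Stage heading, and nothing limits the first-stage tests to laboratory work.

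**Student's t-test can mean the paired form.** True. In that case only the Mann-Whitney branch and the target of the normality check are at fault, and the unpaired-t figures do not apply.

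**The first table overstates the fall.** Fixing the effect in SDs of the differences makes the raw effect shrink from 1.26 SD at rho 0 to 0.56 SD at rho 0.8. At a fixed raw effect the unpaired tests do not get worse; they fail to gain. That is a fair description, and the second table shows it. The gap between paired and unpaired remains.

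**The two-step procedure itself was not simulated.** Also fair. With lognormal data of log SD 1 (an assumption), Shapiro-Wilk rejects in only about 71% of single samples of 12, so the t branch would often be used. The tables describe each branch, not the mixture.

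**The experimental-unit sentence is a separate matter.** Treating repeated samples as independent could produce extra false positives, the opposite direction. No size has been computed for it. It is a request for clarification.

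**Conclusion.** The concern holds. The plan names an independent-samples test for the stage under which the crossover is described, and it names no paired test for that stage. For any crossover outcome analysed by this rule, positive within-person correlation makes the test conservative and costs power. The loss is nil at rho 0 to 0.1, small at 0.2 and substantial from about 0.5. At 0.5, power is 57% (unpaired t) against 80% (paired t), and 52% (Mann-Whitney) against 76% (signed-rank).

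The direction depends on the correlation being positive. The size depends on a correlation the documents do not give and on the assumed effect. The paired t-test holds its nominal level at every correlation tested; the unpaired tests do not.

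The mismatch between test and design is certain from the text. Which endpoints it reaches is not, because the plan leaves that open. The correction should be made before analysis.

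**What to change.** - **First stage:** for every crossover outcome, compare the products within participant. Use a paired t-test, or the Wilcoxon signed-rank test in place of Mann-Whitney, and check normality on the within-person differences.
- **Second stage:** for crossover outcomes, make participant the subject factor, with product and time as within-participant factors, and remove the statement that each sample is the experimental unit.
- **Endpoints:** state which stage covers plasma and urine metabolites, IL-6, TNF-alpha, glucose, insulin and the in vitro enzyme assays.
- **Optional:** a mixed model with product and participant, using the baseline sample already collected. A period term can be added only if both product orders were used, which the documents do not state.

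The cost is a change of analysis wording. No new data are needed.

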The glycemic and insulinemic values obtained experimentally will be recorded in a database. The area under the curve (AUC) will be calculated according to the equation proposed by Wolover and Jenkins (1986) (Eq.4.7.):

$$AUC = \left(\left(A + B + \frac{D}{2} \right) * 15 \right) + \left(\left(\frac{D}{2} + \frac{E}{2} \right) * 30 \right) + \left(\left(\frac{E^2 * 30}{2} \right) * (E + F) \right) \quad \text{Ec 4.7.}$$

Where A, B, C, D, E, F; represent the increase in glucose and insulin above baseline and 15 and 30 represent the time interval between blood samples. Any area below the fasting level will be discarded.

TECNOLÓGICO
NACIONAL DE MÉXICO

EXPECTED RESULTS

ITESO, Universidad
Jesuita de Guadalajara

This research aims to identify which metabolites are bioavailable in plasma and urine samples after ingestion of a hibiscus drink and to identify inflammation markers in the same normal-weight volunteers, as a potential adjuvant in the management of inflammation caused by COVID-19 disease, and generate a hypoglycemic effect by reducing the levels of glucose and serum insulin, consequent to the generation of possible modifications on the physiological mechanisms, including the inhibition of the activity of the α -amylase and α -glucosidase enzymes by the action of the bioactive compounds, as well as by the interaction with the rest of the ingredients that compose the beverage of interest.

- Abdel-Rahman, R. F., Hessin, A. F., Abdelbaset, M., Ogaly, H. A., Abd-Elsalam, R. M., & Hassan, S. M. (2017). Antihypertensive Effects of Roselle-Olive Combination in L-NAME-Induced Hypertensive Rats. *Oxidative Medicine and Cellular Longevity*, 2017. <https://doi.org/10.1155/2017/9460653>
- Abubakar, S. M., Ukeyima, M. T., Spencer, J. P. E., & Lovegrove, J. A. (2019). Acute effects of hibiscus sabdariffa calyces on postprandial blood pressure, vascular function, blood lipids, biomarkers of insulin resistance and inflammation in humans. *Nutrients*, 11(2). <https://doi.org/10.3390/nu11020341>

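### Pre-drink blood and urine are collected at both visits, but the plan gives them no role in the cytokine and metabolite comparisons, so visit-to-visit differences stay in the error

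*Combined protocol and SAP*

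**What the plan says.** Under Acute Trial Clinical Intervention, part (a) Urine, "a basal sample (T=0) was taken in a collection bottle", with later samples at 3, 6, 12 and 24 h. Part b) Blood describes eight venous samples, "the first on arrival of the patients at basal time" and seven more from 30 min to 6 h. This series serves IL-6 and TNF-alpha "and for the bioavailability of phenolic compounds and organic acids, blood samples were taken". The design is a two-period crossover: "After a washout period of more than 6 days, the participants underwent a second intervention with a different product from the first one", "and the samples were repeated according to the following scheme". A pre-drink value is therefore due on each product day.

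Statistical analysis: first stage applies Shapiro-Wilk and then a Student's t or Mann-Whitney test, which "will be used to evaluate the statistical differences between the variables". It does not say whether the variable is a raw value, a change, an AUC or a peak, and it names no baseline term and no pairing. Statistical analysis: second stage adds a repeated-measures ANOVA without stating its endpoints, its factors or whether the basal time is a level.

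Baseline has a stated use in one place only. Under Calculation of the area under the curve, the terms of the equation "represent the increase in glucose and insulin above baseline". For urine metabolites, the only normalisation described in the HPLC-DAD-MS section is by the volume excreted in each interval.

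**The concern.** The visits are more than 6 days apart. A participant can arrive with a different IL-6 level, or a different dietary phenolic background, on the two days. The drink cannot have caused that difference. If post-drink values are compared without reference to it, the part that persists through the visit stays in the product contrast. Taking more samples within the same visit does not average it out.

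Specific objectives 3 and 4 (bioavailability and immunomodulatory potential) rest on these endpoints. With 12 people the pre-drink averages on the two days can differ noticeably by chance, and the plan states no way to account for it although the samples are in the schedule.

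**Working it through.** The documents give no power, effect size or variance, so there is no figure of theirs to reproduce.

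**Inputs.** From the documents: n=12, alpha 0.05, one pre-drink and seven post-drink blood samples per visit. Assumed: two-sided testing, normal data, and the correlation r between the pre-drink and post-drink product differences.

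**1. What a chance gap does.** Set the variance of one measurement to 1 and split it into subject 0.5, visit-day 0.3 and residual 0.2 (all assumed).
- For a single post-drink value, r = 0.3/(0.3+0.2) = 0.6. The regression slope is also 0.6.
- The SD of the mean pre-drink gap between product days is sqrt(2 × 0.5/12) = 0.29.
- In 100,000 simulated trials with no product effect, a paired post-drink test rejected in 5.0%.
- In the 4.6% of trials with a gap of 0.5 to 0.6 SD, the average apparent effect was 0.33 SD (0.6 × 0.55 = 0.33) and 13.6% rejected.
- With a gap under 0.1 SD, 2.0% rejected.

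The error rate is therefore right on average, while the single trial that is run carries a shift of slope × imbalance.

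**2. What adjustment gains.** The reference is a paired t-test on post-drink differences with standardised effect 0.889, which has 80% power at n=12. The alternative regresses the post-drink difference on the pre-drink difference and tests the intercept on 10 degrees of freedom (100,000 runs per r).

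| r | Adjusted power |
|---|---|
| 0 | 75% |
| 0.2 | 77% |
| 0.33 | 80% |
| 0.5 | 86% |
| 0.6 | 91% |
| 0.7 | 95–96% |

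Type I error is about 5% throughout.

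**3. A seven-sample post-drink mean.** Let s be the share of within-person variance common to all samples of a visit (assumed). Scaled to the within-person variance of one sample:
- variance of the post-drink mean = s + (1−s)/7
- r = s/sqrt(s + (1−s)/7)
- slope on the pre-drink difference = s
- variance of a plain change score = (1−s)(1 + 1/7)

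| s | r | Slope | Variance, post-drink mean | Variance, change score |
|---|---|---|---|---|
| 0.3 | 0.47 | 0.30 | 0.40 | 0.80 |
| 0.5 | 0.66 | 0.50 | 0.57 | 0.57 |
| 0.7 | 0.81 | 0.70 | 0.74 | 0.34 |

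The shift follows the slope, not r. A plain change score loses precision whenever s is below 0.5, that is, r below about 0.66. At s=0.3 it has twice the variance. For a single post-drink sample its break-even is r=0.5, and its power in the setting of step 2 is 51% at r=0, 60% at 0.2 and 80% at 0.5. Urine has four post-drink samples, so the seven-sample values do not carry over to it.

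**4. Pairing, for scale.** With an assumed subject share of 0.5, the smallest difference detectable with 80% power is 1.20 SD for an unpaired t-test and 0.89 SD for a paired one. Adjustment moves 0.89 to 0.82 at r=0.5 and to 0.76 at r=0.6. At r=0 it moves it to 0.95.

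**The case against.** The strongest reply is that the plan is silent, which is not the same as excluding baseline. The variable compared in the first stage is undefined and could be a change or an incremental AUC. The second-stage ANOVA could cover the blood series with T=B as a level, and its product-by-time term would then use the baseline. This stands: a reader might infer that the plan has decided to discard the basal samples, and the documents do not show that. Nor do they confirm any use of them, and that missing specification is the point made here.

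A second reply is that the benefit is assumed. That also stands. Below r of about 0.33 adjustment loses a few points of power. Breakfast and lunch fall within the sampling period, so a fasting value may track the later samples less well than the shared-visit model supposes. After a 10–12 h fast, drink-specific metabolites may sit near or below detection (an assumption). The covariate would then be almost constant, and a log of zero is undefined.

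A third reply is that the missing pairing probably costs more. It does under the assumptions above. It is a separate defect, and curing it alone leaves the visit-day noise in place.

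**Conclusion.** The point holds as a gap in specification that costs precision, chiefly for IL-6, TNF-alpha and metabolites measurable before the drink. Three stronger readings are not supported.

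- A reader might infer that false positives are inflated. They are not: the error rate is 5% over repeated trials when pre-drink gaps arise by chance.
- A reader might infer that a pre-drink gap passes into the estimate in full. Only slope × gap does: 0.30, 0.50 or 0.70 of it for a seven-sample mean at s = 0.3, 0.5 or 0.7.
- A reader might infer systematic bias because no randomised product order is stated. The documents do not state a fixed order either, so this remains an open question.

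The gain is about 6 points of power at r=0.5 and 11 at r=0.6, against a loss of about 5 at r=0. These figures are relative to a paired analysis, which the plan does not name, and they rest on an r that the documents do not give.

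**What to change.** Add to the statistical analysis section, before the data are compared by product:

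1. For IL-6, TNF-alpha and each metabolite measurable before the drink, name one post-drink summary per visit (AUC or mean), on the log scale where values are positive and skewed.
2. Analyse the within-participant hibiscus-minus-placebo difference in that summary, with the pre-drink difference as covariate (T=B for blood, T=0 for urine). Leave the covariate centred at zero difference, not at its sample mean, so that the intercept is the product effect. For urine, first define the collection interval to which T=0 refers, so that it can be put on the volume-normalised scale.
3. Include period if both product orders were used.
4. Show the unadjusted paired result beside the adjusted one.
5. For metabolites near or below detection before the drink, use the paired unadjusted comparison. State the rule that assigns each metabolite to one group or the other.
6. Do not make plain change scores the main analysis.
7. State which endpoints, factors and time levels the second-stage ANOVA covers.

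The cost is a change of wording, since the samples are already scheduled. The covariate takes one degree of freedom (11 to 10), a period term takes one more, and a few points of power are lost if r is low.
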